### **8.3.6. Immunogenicity Analyses**

Immunogenicity as assessed by incidence of ADAs will be summarized descriptively.

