- t. Urinalysis: Dipstick (pH, specific gravity, glucose, protein, ketones, blood). Microscopic analysis in the event of abnormal dipstick results (urinary sediment, red blood cells, white blood cells, casts, crystals, epithelial cells, bacteria).
- u. Screening/baseline MRI is to occur as close to the beginning (Day -28) of the window as possible and at least 10 days prior to enrollment, for those who have not had a brain MRI in the 90 days preceding the first dose on Day 1/Week 1.
- v. Perform COAs prior to any potentially stressful procedure (eg, LPs, imaging).
- w. Additional ADA samples should be collected in participants with signs and symptoms of infusion-related reactions. A corresponding additional PK sample should be obtained at the same timepoint.
- x. Informed consent and confirmation of eligibility must be received prior to performing PET scans.
- y. Participants who discontinue due to ARIA may be requested to have an LP per Investigator discretion.
- z. Per footnote v, COAs should be performed prior to LP. If possible, LP should not be performed on the same day when COAs are performed. Participants will be required to stay in the clinic or hospital for a minimum of 30 minutes after the procedure. LPs performed during the screening/baseline period will be performed at least 5 days prior to the expected Day 1/Week 1 dosing visit. LP should not be performed unless results from coagulation laboratory assessments were within clinically acceptable limits within 4 weeks ±5 days.
- aa. If an ET Visit is initiated, the final optional CSF sampling should be performed at that visit. If an ET is not initiated, optional CSF sampling should be performed at [REDACTED].
- bb. For participants in countries where local regulations allow, baseline (optional) Tau PET imaging should be performed prior to dosing on Day 1/Week 1 unless obtained within 24 weeks before Day 1/Week 1 in study AL002-2. In some cases, the initial (baseline) Tau PET scan may be performed after dosing with study drug has commenced. Sponsor agreement will be needed for baseline Tau PET scans occurring after dosing has commenced. Participants who receive an optional Tau PET scan at baseline will receive 1 or more repeated scans after beginning study drug. PET imaging has a window of ±28 days (longer than the standard visit window).

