2. STUDY OBJECTIVES AND ENDPOINTS

The study objectives and endpoints are provided in [Table 2-1](#).

Table 2-1. Study Objectives, Endpoints and Estimands for LTE

| Primary Objectives | Primary Safety Endpoints and Primary Estimand |
|--|---|
| 
To evaluate the long-term safety and tolerability of AL002 in participants with AD.
 | 
Part 1: Primary Safety Endpoint and Estimand:
 
 • Treatment condition: Group T-T (AL002 15 mg/kg, 40 mg/kg or 60 mg/kg IV Q4W) continues their Core Study treatment in the LTE Study; Group P-TC treated with Placebo in the Core study will be titrated to 60 mg/kg of AL002 in the LTE study. • Target population: adult participants with AD excluding apolipoprotein E (APOE) epsilon 4 (e4)-homozygous (e4/e4) participants. • Primary endpoints: AESI incidence and SAE incidence over all weeks. • Accounting for intercurrent events: a composite strategy will be used to handle intercurrent events as below: 
 ○ Hypothetical strategy for handling premature study drug discontinuation for any reason (AEs with a start date more than 90 days after study drug discontinuation are not counted) ○ Treatment policy strategy for handling all other intercurrent events. • Population-level summaries: the descriptive statistical summaries for each treatment group of incidence rates for all AESIs and SAEs over similar periods of time. 
Part 2: Primary Safety Endpoints:
 
 • Changes from baseline (CFBs) in vital signs, physical findings, neurological findings, ophthalmological findings, ECG findings, and clinical laboratory results. • MRI abnormalities (ARIA events) • C-SSRS. 
Primary Estimand for Safety Endpoints Above:
 
The estimand for the Part 2 endpoints is defined with similar attributes as for the Part 1 estimand except applied to the different endpoints
 |

| Primary Objectives | Primary Safety Endpoints and Primary Estimand |
|--|---|

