| 
To evaluate the effects of AL002 on biomarkers in participants with AD
 | 
Biomarker Endpoints
 
 • CFBs in levels of sTREM2 in CSF and/or plasma. • CFBs in levels of biomarkers related to microglia function in CSF and/or plasma including but not limited to CSF1R, IL1RN, osteopontin, and YKL-40. • CFBs in levels of biomarkers related to AD pathology in CSF and/or plasma including but not limited to Aβ40, Aβ42, pTau, and tTau. • CFBs in levels of neurodegeneration biomarkers in plasma and CSF including but not limited to NfL. • CFBs in brain volume, assessed by volumetric MRI. • CFBs in brain pathological tau burden as assessed by Tau-specific PET, only for participants who agree to participate in the optional assessment. • CFBs in brain amyloid burden as assessed by longitudinal Amyloid PET scanning, only for participants who agree to participate in the optional assessment. 
For the exploratory biomarker endpoints, the Main Estimand for exploratory efficacy endpoints applies for LTE analyses, which has the same definition as the Main Estimand for Efficacy.
 
For integrated analyses, however, differences between Placebo and AL002-treated groups are analyzed for Core study data adding the LTE screening data for placebo and the LTE data for Group T-T, and the applicable estimand is the main estimand applied to estimated CFB differences between placebo and treated groups.
 |
| 
To evaluate the effect of immunogenicity to AL002 in participants with AD
 | 
 • Incidence of ADAs. 
For this endpoint, the estimand for safety endpoints applies.
 |

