6.6 Immunogenicity Endpoints

- Incidence of ADAs
- Titers of ADAs.

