^a Target Day and Core Study Day are based on Core Study Day 1.

^b LTE Day 1 represents Core Study Day of first dose date of LTE Study. If no such date, use Core study day of the last visit date among Core visits and LTE screening visit.

Table 7-21. Analysis Visit Windows for ADA (Serum) Assessments Based on LTE Study Day ^a

| Analysis Visit | Target Day | Analysis Visit Window |
|----------------|------------|-----------------------|
| LTE Baseline | 1 | ≤ 1 |
| LTE Week 4 | 29 | [2, 43] |
| LTE Week 8 | 57 | [44, 85] |
| LTE Week 16 | 113 | [86, 141] |

| | | |
|-------------|-----|------------|
| LTE Week 24 | 169 | [142, 211] |
| LTE Week 36 | 253 | [212, 295] |
| LTE Week 48 | 337 | [296, 365] |
| LTE Week 56 | 393 | > 365 |

^a Target Day and LTE Study Day are based on LTE Study Day 1.

Table 7-22. Analysis Visit Windows for PK (Serum) Assessments Based on Core Study Day ^a

| Analysis Visit | Target Day | T-T Analysis Visit Window | Placebo Analysis Visit Window ^b |
|----------------|------------|---------------------------|--|
| Day 1 | 1 | ≤ 1 | ≤ 1 |
| Week 1 | 8 | [2, 12] | [2, 12] |
| Week 2 | 15 | [13, 22] | [13, 22] |
| Week 4 | 29 | [23, 36] | [23, 36] |
| Week 6 | 43 | [37, 50] | [37, 50] |
| Week 8 | 57 | [51, 71] | [51, 71] |
| Week 12 | 85 | [72, 99] | [72, 99] |
| Week 16 | 113 | [100, 141] | [100, 141] |
| Week 24 | 169 | [142, 211] | [142, 211] |
| Week 36 | 253 | [212, 295] | [212, 295] |
| Week 48 | 337 | [296, 351] | [296, min (351, LTE Day 1)] |
| Week 52 | 365 | [352, 379] | [352, min (379, LTE Day 1)] |
| Week 56 | 393 | [380, 407] | [380, min (407, LTE Day 1)] |
| Week 60 | 421 | [408, 435] | [408, min (435, LTE Day 1)] |
| Week 64 | 449 | [436, 463] | [436, min (463, LTE Day 1)] |
| Week 68 | 477 | [464, 491] | [464, min (491, LTE Day 1)] |
| Week 72 | 505 | [492, 519] | [492, min (519, LTE Day 1)] |
| Week 76 | 533 | [520, 547] | [520, min (547, LTE Day 1)] |
| Week 80 | 561 | [548, 575] | [548, min (575, LTE Day 1)] |
| Week 84 | 589 | [576, 603] | [576, min (603, LTE Day 1)] |
| Week 88 | 617 | [604, 631] | [604, min (631, LTE Day 1)] |
| Week 92 | 645 | [632, 659] | [632, min (659, LTE Day 1)] |
| Week 96 | 673 | [660, 687] | [660, min (687, LTE Day 1)] |
| Week 100 | 701 | [688, 715] | [688, LTE Day 1] |
| Week 104 | 729 | [716, 743] | |
| Week 108 | 757 | [744, 785] | |

| | | | |
|----------|------|-------------|--|
| Week 116 | 813 | [786, 841] | |
| Week 124 | 869 | [842, 911] | |

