7.1.3.2 Safety and PD Biomarker Data

Depending on the statistical analysis method, a single value may be required for each analysis visit window (e.g., CFB by visit usually requires a single value), except for “>90 Days Post Last Dose” analysis visit window.

For safety data, if multiple valid, non-missing, continuous records exist in a post-baseline analysis visit window, records will be chosen based on the following rules if a single value is needed, unless otherwise specified:

- The record closest to the target day (in terms of days) for that visit will be selected.
- If there are multiple records that are equidistant from the target day (in terms of days), the later record will be selected.
- If there are multiple records on the same day (regardless of time), the average will be taken.

For exploratory PD biomarker data, if multiple valid, non-missing, continuous records exist in a post-baseline analysis visit window, then the average of these records will be taken.

For safety and exploratory PD biomarker data, if multiple valid, non-missing, categorical records exist in a post-baseline analysis visit window (not applicable to categorical measurements derived from continuous measurements), records will be chosen based on the following rules if a single value is needed, unless otherwise specified:

- The record closest to the target day for that visit (in terms of days) will be selected.
- If there are multiple records that are equidistant from the target day (in terms of days), the later record will be selected.
- If there are multiple records on the same day, the record with the worst severity will be selected, for example:
 - higher grade severity will be selected over lower grade severity for toxicity grades;
 - “low” or “high” will be selected over “normal” for a test or exam with those categories;
 - “abnormal” will be selected over “normal” for a test or exam with those two categories;
 - “positive” will be selected over “negative” for a test or exam with those two categories.

For those categorical measurements derived from continuous measurements, if multiple valid, non-missing, continuous records exist in an analysis visit window, the rules for selecting a single value for continuous measurements apply first, then the corresponding categorical measurements will be derived based on the single selected continuous measurements.

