7.8.1 Antidrug Antibodies (ADAs)

Blood serum samples will be collected for determination of ADAs. In addition to titer numerical results, blood serum results will be classified as Positive, Negative or Unknown (missing, non-evaluable, etc.).

The number and percentage of participants having positive or negative results will be summarized by visit and treatment group. The titer numerical results will be descriptively summarized by visit and treatment group. Shift from baseline in blood serum classes will be summarized by visit (refer to Table 7-20 and Table 7-21 for analysis visit window definitions) and treatment group using the frequency count and percentage of participants in each category.

A listing of ADAs including all participants with available ADA data will be provided.

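### SAP 7.8.1 summarises ADA only by visit, so the stated ADA incidence is never estimated, and some infusion-reaction samples can fall out of the by-visit tables

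*SAP*

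**What the plan says.** Protocol 8.3.6 states the aim: "Immunogenicity as assessed by incidence of ADAs will be summarized descriptively". SAP 6.6 lists "Incidence of ADAs" and ADA titers as the immunogenicity endpoints. SAP Table 2-1 adds, for ADA incidence: "For this endpoint, the estimand for safety endpoints applies". That estimand is set out in Part 1 of the same table: "Primary endpoints: AESI incidence and SAE incidence over all weeks".

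SAP 7.8.1 then gives the analysis: "The number and percentage of participants having positive or negative results will be summarized by visit and treatment group". It also plans descriptive titers by visit, shifts from baseline by visit, and a listing of all available ADA data. It has no summary over the whole post-baseline period and no definition of treatment-emergent ADA.

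Two further provisions bear on which samples are counted. Protocol Table 9, footnote w, says: "Additional ADA samples should be collected in participants with signs and symptoms of infusion-related reactions". SAP 7.1.3.2 says, for several categorical records in one post-baseline window: "The record closest to the target day for that visit (in terms of days) will be selected". The worst record is preferred only among records from the same day.

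**The concern.** The percentage positive at a visit is a point prevalence. Incidence over the study needs each participant counted once if ever newly positive. By-visit percentages cannot be combined into that figure, because the positives at two visits may be the same people or different people. The shift table has the same limit.

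The omission stands out because the SAP gives both a by-visit and an overall summary for C-SSRS (7.4.4), ECG criteria (7.4.6), clinically significant vital signs (7.4.7), ARIA (7.4.8), eye findings (7.4.9) and neurological findings (7.4.10).

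The selection rule adds to it. Protocol 7.10 and footnote w call for an extra ADA sample when a participant reacts to an infusion, and protocol 1.3 names both infusion-related reactions and immunogenicity as potential risks. If that sample is far from a target day, the by-visit tables report the scheduled sample instead.

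**Working it through.** The documents state no ADA rate, so there is no figure to reproduce. The check has three parts.

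**1. Which LTE infusions have an ADA visit.** SAP 6.2.1 gives 13 infusions over 48 weeks: 48/4 + 1 = 13, on LTE Days 1, 29, 57, ..., 337. SAP Table 7-21 has seven post-baseline ADA visits: LTE Weeks 4, 8, 16, 24, 36, 48 and 56. These are SAP analysis weeks, one less than the protocol's nominal weeks. The ADA row of protocol Table 9 is redacted, so the absence of a scheduled sample elsewhere is inferred from these windows.

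**2. What happens to a reaction sample.** Take one positive sample on the infusion day, with all scheduled samples present, on target and negative. The Table 7-21 row "LTE Week 8 | 57 | [44, 85" (window Days 44 to 85, target Day 57) shows the pattern.

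| Infusion day (LTE week) | Window | Target | Distance |
|---|---|---|---|
| 85 (12) | 44–85 | 57 | 28 |
| 141 (20) | 86–141 | 113 | 28 |
| 197 (28) | 142–211 | 169 | 28 |
| 225 (32) | 212–295 | 253 | 28 |
| 281 (40) | 212–295 | 253 | 28 |
| 309 (44) | 296–365 | 337 | 28 |

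The scheduled sample is at distance 0 and is selected each time. That is 6/13 = 46%.

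- At Weeks 4, 8, 16, 24, 36 and 48 the reaction sample shares its day with the scheduled sample, and the same-day rule keeps the positive.
- A Day 1 post-infusion sample falls in the baseline window (Day 1 or earlier). If the rule in SAP 7.1.2.1 applies, negative is preferred to positive there. Table 7-21 has no post-dose Day 1 visit to hold the sample either. Including it gives 7/13 = 54%.
- For Group T-T, Table 7-20 and 38 infusions (148/4 + 1) give 20/38 = 53%, or 21/38 = 55% with Core Day 1.
- If the sample is taken the next day, all are displaced when visits are exactly on target. With visits spread evenly over ±5 days, the sample is kept at an ADA visit only if that visit was early (5 of 11 possible days). The loss is then 1 − (6 × 5/11)/13 = 79% for the Titration Cohort and 1 − (17 × 5/11)/38 = 80% for Group T-T.

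**3. How far by-visit figures leave incidence open.** Let p be the percentage positive at each of the 7 LTE visits; p is an assumption. If the same people are positive throughout, incidence is p. If visits are independent, it is 1 − (1 − p)^7.

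| p | Same people | Independent |
|---|---|---|
| 2% | 2% | 13.2% |
| 5% | 5% | 30.2% |
| 10% | 10% | 52.2% |

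At p = 5%, if every positive were a different person, incidence would be 7 × 5% = 35%. The by-visit percentages would be identical in all three cases.

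**The case against.** The plan offers more than percentages: titers, shifts and a full listing are there, and the shift table separates new from pre-existing positives at each visit. That is correct, but each of these summaries is still by visit, and a listing estimates nothing.

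A reader might infer that most reaction samples are discarded. With same-day sampling the closest-to-target rule displaces 46% in the Titration Cohort and 53% in Group T-T. It becomes a clear majority only with next-day sampling. The count also gives every infusion equal weight, and the documents give no reaction timing by dose. Same-day positives at the second and third LTE infusions are kept. A reaction sample is also kept if the scheduled sample in its window is missing.

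A reader might also infer that the immunogenicity result is biased low where it matters most. The documents do not support that. If ADA persists, a positive on Day 85 shows again at the scheduled Day 113 sample; only a transient positive is lost. By-visit prevalence also includes participants positive at baseline, so it need not lie below a treatment-emergent rate.

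Nor does the point call for worst-case selection within each window, as SAP 7.4.8 uses for ARIA. That would report a Day 85 sample as Week 8, 28 days off target, and raise by-visit rates selectively among participants who reacted. Any-time incidence needs no change to the rule.

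Finally, the endpoint is exploratory and descriptive, with no test attached. That limits the severity but does not supply the missing estimate.

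**Conclusion.** The point holds in two parts. First, the plan names ADA incidence under an over-all-weeks estimand and produces no participant-level figure for it; this follows from the text and rests on no assumption. Second, the selection rule can leave unscheduled reaction samples out of the by-visit tables. It does so at 6 of 13 LTE infusions (46%) for the Titration Cohort, assuming that samples are taken on the infusion day, that the scheduled sample in the window exists, and that the SAP windows reflect the redacted schedule.

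Together these mean that a transient positive can be missing from every summary table while still appearing in the listing. The effect on the reported ADA rate cannot be derived, because the documents give no ADA rate, persistence or reaction frequency. The percentages in part 3 of the working illustrate the ambiguity and do not forecast this trial. This should be changed, but it does not threaten the primary conclusions.

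**What to change.** In SAP 7.8.1, add by treatment group the number and percentage of participants with treatment-emergent ADA. Define it as negative at baseline (Core baseline for Group T-T, LTE baseline for the Titration Cohort) and positive at any evaluable sample after the first AL002 dose, scheduled or unscheduled. State that samples taken after the first infusion on Day 1 count as post-baseline. Report baseline-positive participants separately. Keep the by-visit tables and their selection rule as supportive.

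The text should also say whether the limit of 90 days after the last dose, used elsewhere for safety data, applies here.

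The cost is SAP wording and one added summary from data already collected. The reported ADA rate may rise.

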8. ANALYSES TO BE PERFORMED AT INTERIM

In general, analyses outlined in this SAP apply to the final analysis, when the LTE study concludes.

The scope of the first IA at the time of unblinding of the Core Study is specified in Section 8.1.

The scope of the subsequent IAs will be the same (Section 8.1), except that the inferential statistical analysis (Section 7.6.2) will be performed when there is sufficient data at the data cutoff date of the IA.

8.1 Interim Analyses at the Time of Unblinding of the Core Study

The analyses specified in this section will be performed at the time of unblinding of the Core Study. For each summary, the corresponding by-participant listing will be provided.

8.1.1 Participant Disposition, Demographics and Baseline Characteristics

Participant disposition specified in Section 7.2.1 will be summarized for the ATS.

Demographics and baseline characteristics specified in Section 7.3.1 will be summarized for the ATS-LTE.

8.1.2 Efficacy Analyses

For each efficacy endpoint, the integrated descriptive summary and the longitudinal trend figure specified in Section **Error! Reference source not found.** will be provided for the main estimand in the FAS.

8.1.3 Safety Analyses

The integrated summary of extent of exposure to study drug as specified in Section 7.4.1 will be provided for the Non-e4/e4 Set.

The following integrated summaries of TEAE will be provided overall across two studies and by the time interval of TEAEs occurrence as specified in Section 7.4.1.2.1 for the Non-e4/e4 Set:

- Summary of TEAEs
- Incidence of TEAEs by Preferred Term
- Incidence of TEAEs Leading to Early Study Drug Discontinuation by System Organ Class and Preferred Term
- Incidence of Treatment-Emergent SAE by Preferred Term

For the integrated summaries of TEAE by time interval of TEAEs occurrence, the same TEAE counting rules apply per each time interval.

The integrated summaries of ARIA as specified in Section 7.4.8 will be provided for the Non-e4/e4 Set.

The integrated descriptive summaries of continuous safety endpoints as specified in Section 7.4.1.2 will be provided for the Non-e4/e4 Set for the laboratory data, ECG, and Vital Signs. Integrated summaries of treatment-emergent potentially clinically significant values will be provided for the Non-e4/e4 Set for ECG and Vital Signs.

PK, ADA, C-SSRS, eye exam, neurological exam, or other safety analysis may be performed at interim analyses after the first IA.

8.1.4 Biomarker Analyses

For CSF and plasma biomarkers, volumetric MRI, amyloid PET and Tau PET parameters [Table 7-39], the integrated descriptive summaries [tables] specified in Section 7.7.2 **Error! Reference source not found.** will be provided for the main estimand in the FAS.

9. STATISTICAL SOFTWARE

SAS® Version 9.4 or later in the UNIX environment will be used for all statistical analyses.

